## **6.3.2** Blinding and Code-breaking Procedures

The VYF03 study is a Phase II, randomized, observer-blind, active-controlled, non-inferiority study to the Stamaril control vaccine.

The study will be performed in a modified double-blind fashion: Sponsor, Investigators and Study staff who conduct the safety assessments, and the participant will not know which vaccine is administered.

Only the study staff who prepare and/or administer the vaccine and who are not involved in safety evaluations ("vaccinator") will know which vaccine is administered. The "vaccinator" or authorized designee will have to ensure that the documents on randomization are stored in a secure place where only he/she has access.

The code may be broken in the event of an AE only when the identification of the vaccine received could influence the treatment of the participant. Code-breaking should be limited to the participant(s) experiencing the AE.

The blind can be broken by the Investigator or a delegate through the IRT system, as explained in the code-breaking procedures described in the Operating Guidelines. Once the emergency has been addressed by the site, the Investigator or a delegate must notify the Sanofi Pasteur Responsible Medical Officer (RMO) if a participant's code was broken. All contact attempts with the Sponsor prior to unblinding are to be documented in the source documents, and the codebreaking case report form (CRF) is to be completed.

The Institutional Review Boards (IRB)/Independent Ethics Committees (IEC) must be notified of the code-breaking, in accordance with local regulations. All documentation pertaining to the event must be retained in the site's study records, and in the Sanofi Pasteur files. Any intentional or unintentional code-breaking must be reported, documented, and explained, and the name of the person who requested it must be provided to the Sponsor.

A request for the code to be broken may also be made:

- by the Global Pharmacovigilance (GPV) Department through an internal system for reporting to Health Authorities in the case of an unexpected SAE considered causally related, as described in International Council for Harmonization (ICH) E2A. In this case, the code will be broken only for the participant(s) in question. The information resulting from code-breaking (ie, the participant's vaccine or group assignment) will not be communicated to either the Investigator or the immediate team working on the study, except for the GPV representative.
- by the IDMC if needed to facilitate their assessment of safety.

The code-breaking procedures are described in the Operating Guidelines.

# **6.4** Study Intervention Compliance

The following measures will ensure that the study intervention is administered as planned (see Table 6.1), and that any noncompliance is documented so that it can be accounted for in the data analyses:

- All study interventions will be administered by qualified and trained study personnel
- The person in charge of study intervention management at the site will maintain accountability records of study intervention delivery to the study site, study intervention inventory at the site, dose(s) given to each participant, and unused or wasted doses

# 6.5 Concomitant Therapy

At the time of enrollment, ongoing medications and other therapies (eg, blood products) should be recorded in the source document as well as new medications prescribed for new medical conditions / AEs during study participation.

Documentation in the CRF of ongoing concomitant medication(s) will be limited to specific categories of medication(s) of interest beginning on the day of first vaccination. This may include medications of interest that were started prior to the day of vaccination.

Reportable medications will be collected in the CRF from the day of each vaccination to the end of the solicited and unsolicited follow-up period, except for use of any investigational or non-registered product (drug, vaccine or medical device), or vaccination with commercial YF vaccine, which will be collected for the entire study period .

Reportable medications include medications that impact or may impact the consistency of the safety information collected after any vaccination and/or the immune response to vaccination. Three standard categories of reportable medications are defined:

- Category 1: medications impacting or that may have an impact on the evaluation of the safety (eg, antipyretics, analgesics, and non-steroidal anti-inflammatory drugs [NSAIDs], systemic steroids/corticosteroids)
- Category 2: medications impacting or that may have an impact on the immune response (eg, other vaccines, blood products, antibiotic classes that may interfere with bioassays used by the Global Clinical Immunology [GCI] department or other testing laboratories, systemic steroids/corticosteroids, immune-suppressors, immune-modulators with immunosuppressive properties, anti-proliferative drugs such as DNA synthesis inhibitors)
- Category 3: medications impacting or that may have an impact on both the safety and the immune response (eg, systemic steroids/corticosteroids)

Any investigational or non-registered product (drug, vaccine or medical device), other than the study vaccine during the period beginning 29 days before the dose of study vaccine or during the study period, as well as receipt of a commercial YF vaccine, will be recorded as Category 3.

Dosage and administration route, homeopathic medication, topical and inhaled steroids, as well as topical, ophthalmic, and ear treatments will not be recorded. Topical analgesics should not be

applied at the site of vaccination; however, if they are applied inadvertently to the vaccination site, they should be recorded as a Category 1 medication in this specific instance.

Medications given in response to an AE will be captured in the "Action Taken" section of the AE CRF only. No details will be recorded in the concomitant medication CRF unless the medication(s) received belongs to one of the pre-listed categories. Medications will not be coded.

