**Table 1.1: Schedule of activities** 

Phase II Study, 9 or 10 Visits, 1 Vaccination, 8 or 9\* Blood Samples, 5-year Duration Per Participant

Visit/Contact	Collection of information in the CRF	Visit 1	Visit 2†	Visit 3‡	Visit 4	Visit 5	Visit 6	Visit 7	Visit 8	Visit 9	Visit 10
Study timelines (days/months/ years)	N/A	D01	D11	D15	D29	6 M post visit 1	1 Y post visit 1	2 Y post visit 1	3 Y post visit 1	4 Y post visit 1	5 Y post visit 1
_											
	•										
	_	 									

Visit/Contact	Collection of information in the CRF	Visit 1	Visit 2†	Visit 3‡	Visit 4	Visit 5	Visit 6	Visit 7	Visit 8	Visit 9	Visit 10
Study timelines (days/months/ years)	N/A	D01	D11	D15	D29	6 M post visit 1	1 Y post visit 1	2 Y post visit 1	3 Y post visit 1	4 Y post visit 1	5 Y post visit 1
Time windows (days)	N/A	N/A	+2 days	+2 day	+3 days	±15 days	±15 days	±15 days	±30 days	±30 days	±30 days
	I										

Visit/Contact	Collection of information in the CRF	Visit 1	Visit 2†	Visit 3‡	Visit 4	Visit 5	Visit 6	Visit 7	Visit 8	Visit 9	Visit 10
Study timelines (days/months/ years)	N/A	D01	D11	D15	D29	6 M post visit 1	1 Y post visit 1	2 Y post visit 1	3 Y post visit 1	4 Y post visit 1	5 Y post visit 1
Time windows (days)	N/A	N/A	+2 days	+2 day	+3 days	±15 days	±15 days	±15 days	±30 days	±30 days	±30 days
_											

AE: adverse event; AESI: adverse events of special interest, BL: blood sampling; CRF: case report form; D: day; DC: diary card; M: month; MA: memory aid; Min: minutes; mL: milliliter; N/A: not applicable; Pre-vac: pre-vaccination; SAE: serious adverse event; Vac: vaccination

- † Visit 2 to be performed only for the subset of participants submitted to an additional immunogenicity test at D11
- ‡ Visit 3 can be replaced by a phone call only in case the visit cannot be performed at Investigational site (in this case, the physical examination will not be performed)
- § In case of participant discontinuation at a visit, the entire visit will be completed
- \*\*For the entire study period, collection of vaccination with commercial YF vaccine and use of any investigational or non-registered product (drug, vaccine or medical device). Up to Visit 4, collection of concomitant medication.
- ‡‡Only for pregnancies with estimated conception date within the 28 days before or after study vaccination
- †† HIV/Hepatitis B/Hepatitis C serology testing at baseline (Visit 1) will be optional depending on local regulatory requirements.

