## 2.1 Study Rationale

A first study, VYF01, aiming to assess the safety, viremia and immune responses of 3 dosages of vYF, compared to YF-VAX, as a control vaccine, is ongoing in the USA. A second planned study, VYF02, aims to assess the non-inferiority of the immune response of the investigational vaccine candidate vYF to the licensed YF-VAX vaccine in adults in the USA.

The proposed third study, VYF03, is a Phase II, randomized, observer-blind, active-controlled (Stamaril) study to assess the non-inferiority of the immune response, in terms of seroconversion rates, of the investigational vaccine candidate vYF to the licensed Stamaril, in adults aged 18 years up to 60 years in EU. The safety and immunogenicity profile of vYF in a cohort of participants of Chinese origin living in Asia will also be presented. The study will also assess the immunogenicity profiles (seroprotection, GMT and GMTR) and the safety profiles of vYF and Stamaril.

In EU, it is planned to enroll 570 participants into 2 groups in a 2:1 ratio: 380 participants will be administered vYF and 190 participants will be administered Stamaril on D01. In Asia, it is planned to enroll 120 participants also distributed into 2 groups in a 2:1 ratio: 80 participants will be administered vYF and 40 participants will be administered Stamaril on D01.

The persistence of the immune response over time, up to 5 years post-vaccination, will be assessed yearly.

VYF03 assessment will be based on immunogenicity and safety profiles of the vYF vaccine in comparison to Stamaril, which is the current YF vaccine licensed in more than 100 countries (except USA, Canada, and Japan).

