#### 5.2 Exclusion Criteria

Potential participants will be recruited from a pool of volunteers who meet site-specific screening requirements.

Participants are not eligible for the study if any of the following criteria are met:

Participation at the time of study enrollment (or in the 4 weeks preceding the study vaccination) or planned participation during the first 2 years of the 5-year follow-up in another clinical study investigating a vaccine, drug, medical device, or medical procedure. Enrollment in another study after the first 2 years is permitted, assuming that it does not exclude participation in this study.

E02: Receipt of any vaccine in the 4 weeks preceding the study vaccination or planned receipt of any vaccine in the 4 weeks following the study vaccination (prior to visit 4), except for influenza vaccination, which may be received at least 2 weeks before study vaccinesb. This exception includes all influenza vaccines including monovalent pandemic influenza vaccines.

E03: Previous vaccination against a FV diseasec at any time, including YF with either the study vaccine or another vaccine.

E04: Receipt of immune globulins, blood, or blood-derived products in the past 6 months.

E05: Known or suspected congenital or acquired immunodeficiency; or receipt of immunosuppressive therapy, such as anti-cancer chemotherapy, or radiation therapy, within the preceding 6 months; or long-term systemic corticosteroid therapy (prednisone or equivalent for more than 2 consecutive weeks within the past 3 months).

<sup>a for participants aged less than 21 years in Singapore, an informed consent form has been signed and dated by both the participant and the parent(s) or another legally acceptable representative

<sup>b Except for Thai participants, see Appendix 10.5

<sup>c eg, Dengue vaccine, Japanese encephalitis vaccine, Tick borne encephalitis virus (TBE) vaccine, YF vaccine

- E06: Known history of any FV infectionh.
- E07: Known systemic hypersensitivity to any of the vaccine components, eggs, or history of a life-threatening reaction to the vaccines used in the study or to a vaccine containing any of the same substancesa.
- E08: Known history or laboratory evidence of HIV infectionb
- E09: Known history or laboratory evidence of hepatitis B or hepatitis C infectionc

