#### Unsolicited Non-serious Adverse Events

Unsolicited non-serious adverse events will be collected from the day of vaccination (D01) until 28 days after vaccination (D29).

The intensity grading scale for unsolicited non-serious adverse events is presented in Appendix 10.3.5.1.2.

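### After Visit 4 the CRF no longer captures licensed dengue, JE or TBE vaccines, immune globulins/blood products or systemic immunosuppressants, so the M6 and Y1–Y5 titers cannot be flagged for them

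*Protocol*

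**What the plan says.** Protocol 6.5 sets the general rule: "Reportable medications will be collected in the CRF from the day of each vaccination to the end of the solicited and unsolicited follow-up period". The footnote to Protocol Table 1.1 gives the same end point by visit: "Up to Visit 4, collection of concomitant medication". Visit 4 is D29, and Protocol 8.3.1 ends collection of non-serious unsolicited events on the same day.

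Section 6.5 makes an exception for investigational or non-registered products, "or vaccination with commercial YF vaccine, which will be collected for the entire study period".

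The same section defines Category 2 as "medications impacting or that may have an impact on the immune response (eg, other vaccines, blood products" and goes on to list immune-suppressors. It also asks that ongoing medications at enrollment "should be recorded in the source document as well as new medications prescribed for new medical conditions / AEs during study participation".

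At entry, Protocol 5.2 excludes people with prior flavivirus vaccination (E03, with the examples "eg, Dengue vaccine, Japanese encephalitis vaccine, Tick borne encephalitis virus (TBE) vaccine, YF vaccine"), recent immune globulins or blood products (E04), and immunodeficiency or immunosuppressive therapy (E05).

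On follow-up, Protocol 2.1 states: "The persistence of the immune response over time, up to 5 years post-vaccination, will be assessed yearly". Protocol 8.1.2.1 and 9.4.2 and SAP 5.1.2.2 make titers, seroprotection, seroconversion and GMTRs secondary endpoints at M6 and Y1 to Y5, analyzed on the FAS.

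**The concern.** The yearly titers are meant to describe how long the response to a single dose of vYF or Stamaril lasts. The protocol regards certain exposures as relevant to the immune response: it screens for them at entry and names them, or their class, in Category 2. It stops capturing them in the CRF before most of the titers are drawn.

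If a participant receives a licensed JE vaccine in year 2, or starts systemic immunosuppression before the Y3 sample, the later titers reflect the study dose plus that exposure. The analyst has no concomitant-medication field with which to identify these samples, set them aside, or show that they make no difference. What is at stake is how the persistence summaries are read. Systematic collection with dates is easy at the visit and hard to reconstruct years later.

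**Working it through.** The plan states no figure on this point to reproduce. The check compares the collection window with the titer schedule and then looks for any other route into the database.

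**1. Window against schedule**
- Collection window: D01 to Visit 4, D29 (Protocol 6.5, Table 1.1 footnote). That is about 28 of the roughly 1800 days in Table 8.1, and 28/1800 = 1.6%.
- Post-vaccination titer points (Protocol 8.1.2.1): D11 (subset only), D29, M6, Y1, Y2, Y3, Y4, Y5, eight in all.
- Points after Visit 4: M6 and Y1 to Y5, six in all. That is 6 of 8, or 6 of 7 for participants outside the D11 subset.

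**2. Other routes into the CRF**
- *Whole-study exception (6.5, Table 1.1 footnote).* Covers commercial YF vaccine and investigational or non-registered products. A licensed dengue, JE or TBE vaccine is neither.
- *Action Taken on the AE form (6.5).* Requires a collected AE. Under 8.3.1, non-serious unsolicited events stop at D29, SAEs and AESIs are collected to M6, and after that only related or fatal SAEs. Between D29 and M6 a serious illness and its treatment can leave a trace. After M6, treatment for an unrelated, non-fatal illness has no CRF page.
- *COVID-19 form (Appendix 10.5.2).* Concerns COVID-19 vaccines only.
- *Flavivirus serology (8.1.2.2).* Planned on Visit 1 samples only. Testing for other flaviviruses is optional, and could not reveal immune globulin or immunosuppression.
- *Source documents (6.5).* Medications prescribed for new conditions or AEs should be there, which plausibly covers most immunosuppressants and therapeutic immune globulin. A travel or routine vaccine is not clearly within that wording. Source documents stay at the site (Appendix 10.1.8), outside the analysis database.

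**3. Analysis rules**
- The only exclusion for interfering therapy belongs to the PPAS and ends at D29 (Protocol 9.3, SAP 5.2).
- Persistence is summarized on the FAS. Neither Protocol 9.4.2 nor SAP 5.1.2.2 has a rule for titers taken after a later exposure, even for the commercial YF vaccine that is collected.

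**4. Can the effect be sized?**
If a fraction *f* of an arm has an exposure that multiplies the titer by *r*, the arm's GMT is multiplied by *r*^*f*. The documents give neither *f* nor *r*, so no value follows. Two things do follow from the formula:
- With the same *f* and *r* in both arms, the between-arm GMT ratio is multiplied by *r*^*f* / *r*^*f* = 1.
- If half the exposures raise titers by *r* and half lower them by the same factor, the arm's GMT is multiplied by *r*^(*f*/2) × (1/*r*)^(*f*/2) = 1.

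The direction and the size are therefore both open.

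**The case against.** The case for leaving the plan alone is substantial.

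- The exposure acting most directly on YF titers, commercial YF vaccine, is already collected for the whole study. This stands and narrows the gap.
- Source documents should hold many of the prescribed agents. This also stands, so it would be wrong to say these exposures go wholly unrecorded. What remains is mainly licensed preventive vaccines, together with the fact that source notes cannot be analyzed from the database.
- A large rise between visits would not be invisible. From Y1, seroconversion is a 4-fold rise over the previous planned time point, tabulated yearly. Such a rise would be counted, but with no cause attached. Smaller rises, and falls, would not be picked out this way.
- Randomization makes similar exposure in the two arms plausible. This stands in part. Under Protocol 2.3.2, participants can learn their group after the first interim analysis, and the two groups then receive different information about travel vaccination. Different contact with travel vaccination services is an inference, not something the documents report.
- A persistence summary that keeps everyone regardless of later treatment is a legitimate description. Agreed; the point is only that the supportive alternative cannot be produced.

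A reader might also infer that the results by baseline FV status become wrong when an FV-naive participant is later vaccinated against another flavivirus. They do not. SAP 4.2.1.4 defines the stratum by the Visit 1 sample, and the participant remains correctly classified.

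**Conclusion.** The point holds as a limited data-collection gap. Apart from commercial YF vaccine and investigational or non-registered products, Category 2 agents have no concomitant-medication CRF entry after D29. Licensed dengue, JE and TBE vaccines, and immune globulins, blood products or systemic immunosuppressants beyond site notes, cannot be flagged for the M6 and Y1–Y5 titers.

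These exposures may shift those titers. It is tempting to say that they will, or to attach a number, but the documents supply neither a frequency nor an effect size and the net effect could be negligible. The D29 primary endpoint is untouched. The persistence analyses are descriptive, with no hypothesis or success criterion. This is a cheap improvement worth making, not a flaw in the non-inferiority comparison.

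The conclusion rests on Protocol 6.5 and the legible Table 1.1 footnote. The body rows of that table are not visible in the public copy, and the CRF itself was not available.

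**What to change.** In Protocol 6.5 and the Table 1.1 footnote, extend the whole-study CRF exception to any flavivirus vaccine, immune globulins or blood products, and systemic immunosuppressive therapy. Ask at M6 and at each yearly visit, and record the date.

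In SAP 5.1.2.2, keep the FAS persistence summary as planned and add one supportive summary that omits titers taken after a participant's first such event.

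Cost: a protocol and CRF amendment, one or two extra questions in a study that already collects commercial YF vaccine and investigational products throughout, and one more table. The yearly interview becomes slightly longer, and some answers will carry recall error.

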#### 6.5.1 Rescue Medicine

Appropriate medical equipment and emergency medications, including epinephrine (1:1000), must be available on site in the event of an anaphylactic, vasovagal, or other immediate allergic reaction.

# 6.6 Dose Modification

Not applicable.

# 6.7 Intervention After the End of the Study

Not applicable.

# 7 Discontinuation of Study Intervention and Participant Discontinuation/Withdrawal

# 7.1 Discontinuation of Study Intervention

Not applicable as there is only one vaccination.

# 7.2 Participant Discontinuation/Withdrawal from the Study

- A participant may withdraw from the study at any time at his/her own request or may be withdrawn at any time at the discretion of the Investigator for safety, behavioral, compliance, or administrative reasons. This is expected to be uncommon.
- The reason for withdrawal should be clearly documented in the source documents and in the CRF: Adverse Event, Lost to Follow-up, Protocol Deviation, or Withdrawal by Participant.
- The participant will be permanently discontinued both from the study intervention and from the study at that time.
- If the participant withdraws consent for disclosure of future information, the Sponsor may retain and continue to use any data collected before such a withdrawal of consent.
- If a participant withdraws consent, he/she may request destruction of any samples taken and not tested, and the Investigator must document this in the site study records.

• Withdrawn participants will not be replaced. However, all participants enrolled in this study will be followed up for 5 years after vaccine administration. They will be kept in the study (ie, will not be withdrawn) even if they fail to come to one or more of the yearly visits during the 5-year follow-up.

# Follow-up of Discontinuations

For participants who have prematurely terminated the study, the site should attempt to contact them and complete all scheduled safety follow-ups, except if they specified that they do not want to be contacted again and it is documented in the source document.

For participants where the reason for early termination is lost to follow-up, the site will not attempt to obtain further safety information. See Section 7.3 for definition of "lost to follow-up".

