To describe the safety profile of the vYF vaccine in comparison to the safety profile of the control Stamaril To describe the safety of vaccination in all participants up to 28 days after vaccination To describe all serious adverse events (SAEs) up to 6-month follow-up To describe related SAEs and all deaths from D01 to 5 years after vaccination To describe all AESIs up to 6-month after vaccination;	
 
Presence, nature (Medical Dictionary for Regulatory Activities [MedDRA] preferred term), duration, intensity and relationship to vaccination of any unsolicited systemic AEs reported in the 30 minutes after vaccination
 
Presence, time to onset, number of days of presence, and intensity of solicited (pre-listed in the participant's diary and electronic case report form [eCRF]) injection site reactions up to 7 days after vaccination solicited
 
Presence, time to onset, number of days of presence, and intensity of solicited systemic reactions up to 14 days after vaccination
 
Presence, nature (MedDRA preferred term), time to onset, duration, intensity, and relationship to vaccination (for systemic AEs only) of unsolicited (spontaneously reported) AEs up to 28 days after vaccination
 

Objectives	Endpoints		
	
 
Presence of any SAEs and AESIs, up to 6-month after vaccination
 
Presence of related SAEs and all deaths from D01 to 5 years after vaccination
 
		
Exploratory			
To describe the serological status of FV infection (dengue and Zika in all participants in EU and Asia; JE in Asia) in the study population at baseline	NAb levels against FV infection (dengue and Zika in all participants in EU and Asia; JE in Asia) on a blood sample taken at baseline		

AESI: adverse event of special interest; D: day; eCRF: electronic case report form; FV: flavivirus; GMT: geometric means of titers; GMTR: geometric means of titer ratios; M: month; MN; microneutralization; NAb: neutralizing antibody; Y: year

- \* YF-naïve participants (or negative) at baseline correspond to participants with no detectable YF antibody (Ab) titers before vaccination. YF seronegative at baseline is defined as a titer < LLOQ for the assay (any participant with a baseline titer  $\geq$  LLOQ will be eliminated from the primary analysis [Per-protocol analysis]).
- LLOQ determined as 10 (1/dil), also defined the threshold of protection.

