#### 4.4 **End of Study Definition**

A participant is considered to have completed the study if he/she has completed the last visit planned in the SoA.

The end of the study is defined as the date of the last visit of the last participant in the study.

However, for periodic safety reports, the study is considered completed when the clinical study report is finalized.

All participants enrolled in this study will be followed up for 5 years after vaccine administration. They will be kept in the study (and so, will not be withdrawn) even if they fail to come to one or more of the yearly visits during the 5-year follow-up.

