# 7.3 Lost to Follow-up

A participant will be considered lost to follow-up if he or she repeatedly fails to return for scheduled visits and is unable to be contacted by the study site.

The following actions must be taken if a participant fails to return to the site for a required study visit or cannot be contacted as planned in the SoA:

- The site must attempt to contact the participant and reschedule the missed visit as soon as possible, counsel the participant on the importance of maintaining the assigned visit schedule and ascertain whether or not the participant wishes to and/or should continue in the study.
- Before a participant is deemed lost to follow-up, the Investigator or designee must make every effort to regain contact with the participant (where possible, 3 telephone calls and, if necessary, a certified letter to the participant's last known mailing address or local equivalent methods), or at least to determine his/her health status while fully respecting his/her rights. These contact attempts should be documented in the participant's medical record.
- Should the participant continue to be unreachable, he/she will be considered to have withdrawn from the study.

Discontinuation of specific sites or of the study as a whole are handled as part of Appendix 10.1.

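### For participants who cannot be reached in the yearly phase, the retention and lost-to-follow-up rules do not fit together, and safety enquiry stops once lost to follow-up is recorded

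*Protocol*

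**What the plan says.** **Retention.** Protocol Section 4.4 says of all enrolled participants: "They will be kept in the study (and so, will not be withdrawn) even if they fail to come to one or more" yearly visits. Section 7.2 repeats the rule.

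**Lost to follow-up.** Section 7.3 applies the term to a participant "if he or she repeatedly fails to return for scheduled visits and is unable to be contacted by the study site". The steps listed below that definition are triggered by one missed required visit or one failed contact. Before the label is used, the site must make every effort to regain contact ("where possible, 3 telephone calls and, if necessary, a certified letter", or local equivalents), "or at least to determine his/her health status while fully respecting his/her rights". The last step reads: "Should the participant continue to be unreachable, he/she will be considered to have withdrawn from the study".

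**Effect of withdrawal.** Section 7.2 makes withdrawal permanent, for the study as well as the intervention. No re-entry is described.

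**Safety enquiry afterwards.** Under Follow-up of Discontinuations, other early terminators are still contacted for the scheduled safety follow-ups unless they have refused contact. For this one group, "For participants where the reason for early termination is lost to follow-up, the site will not attempt to obtain further safety information".

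**Endpoints concerned.** Table 3.1 has the objective "To describe related SAEs and all deaths from D01 to 5 years after vaccination", and a persistence objective with titres yearly from Y1 to Y5 in all participants. Both are secondary, and Section 9.4.2 makes their analysis descriptive.

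**The concern.** Two site teams facing the same unreachable participant could act differently and each cite the protocol. One, following Sections 4.4 and 7.2, would keep the participant open and call again next year. The other, following the last step of Section 7.3, would close the participant for good.

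The second route leaves a gap. The objective is all deaths to 5 years, but active enquiry ends for the one group whose vital status is unknown at closure. Section 8.3.1 does not fill the gap. After participation ends, investigators need not look for events, and a death they happen to hear of must be notified only if they judge it related. An unrelated death could then go unrecorded even when the site knows of it. The readable text names no registry, next-of-kin or year-5 vital-status check.

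At stake are the completeness of the 5-year death and related-SAE data, some later persistence titres, and comparable follow-up between sites.

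**Working it through.** The plan states no figure on this point that could be reproduced. The check is a reading of the rules side by side, followed by arithmetic on assumed rates.

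**1. Which participants fall under which rule**

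| Situation in the yearly phase | Sections 4.4 and 7.2 | Section 7.3 | Result |
|---|---|---|---|
| Misses visits, can be contacted | Kept | Definition not met | No conflict |
| Misses one visit, unreachable after the required effort | Kept | Definition not met (not repeated), but the last step withdraws | Conflict |
| Misses several visits, unreachable | Kept; no exception stated | Definition met; withdrawn | Reconcilable only if 7.3 is read as an unstated exception |
| Closed as above, then reappears | Withdrawal is permanent | Silent | No route back |

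The missing count matters because the visits are far apart. Take a participant last seen at M6. If one missed visit and failed contact suffice, closure comes after the Y1 window (D360 in Table 8.1). If two missed visits are needed, it comes after the Y2 window (D720). The two readings differ by 720 − 360 = 360 days.

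**2. Deaths**

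Inputs from the documents: 690 participants and 5 years, so 690 × 5 = 3,450 planned person-years. The implied attrition, 1 − 456/570 = 20%, concerns EU evaluability at D29 and cannot serve as a 5-year loss rate.

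Assumptions, not in the documents:
- a share d lost by year 5, with losses spread evenly, so each lost participant misses 2.5 years on average;
- a death rate of 0.1% to 0.2% per year, that is 3.45 to 6.9 deaths expected in all;
- lost participants at equal risk or, as a stress case, at three times that risk.

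Unobserved person-years = 690 × d × 2.5. Missed deaths = that number × annual rate (× 3 in the stress case).

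| d | Vital status unknown at Y5 (690 × d) | Person-years unobserved | Share of 3,450 | Deaths missed, equal risk | Deaths missed, three times the risk |
|---|---|---|---|---|---|
| 5% | 34.5 | 86.25 | 2.5% | 0.1 to 0.2 | 0.3 to 0.5 |
| 10% | 69 | 172.5 | 5% | 0.2 to 0.3 | 0.5 to 1.0 |
| 20% | 138 | 345 | 10% | 0.3 to 0.7 | 1.0 to 2.1 |
| 30% | 207 | 517.5 | 15% | 0.5 to 1.0 | 1.6 to 3.1 |

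These are ceilings on what the rule costs, since re-contact would not find everyone.

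**3. Titres**

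A participant unreachable at Y1 who returns at Y2 could still give four titres (Y2 to Y5) and three yearly ratios (Y3/Y2, Y4/Y3, Y5/Y4). Permanent closure gives these up, and SAP Section 5.3.1 does not impute.

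Avoidable loss = 690 × u × r × 4, where u is the share unreachable at Y1 and r the share of those who would return for all of Y2 to Y5. With u assumed at 3% to 5%, 690 × u is about 21 to 35, giving 84r to 140r person-visits. Nothing in the documents informs r. At r = 1 the loss is 84 to 140 visits; at r = 0 it is none.

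**4. Reporting**

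SAP Table 7.8 reports deaths during the study over participants with available data, and Section 5.3.2 generally replaces no missing safety data. Neither says how a participant lost at, say, Y2 counts in that denominator.

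**The case against.** The strongest reply is that the passages mostly agree once Section 7.3 is read in full. Missing visits alone means retained; repeatedly missing them and being unreachable means lost. A reader might infer that one missed Y1 visit closes the case. The definition does not support that, because it asks for repetition. What stands is narrower: the closing step does not repeat that condition, so a site could close after one missed visit.

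A reader might also infer that the protocol bars safety enquiry altogether. It does not. Section 7.3 requires an attempt to regain contact or establish health status first, and a death that explains the silence is what that step should find. Only enquiry after the label is stopped.

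Nor does the label itself cost most of the titres. A permanently unreachable person gives no blood whatever the record says.

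Finally, visit procedures are in Operating Guidelines that are not available here, and the activity rows of the schedule are missing. Site re-contact practice cannot be fully judged. That is fair, but the no-enquiry sentence is an explicit protocol rule and not something left unsaid.

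**Conclusion.** The point holds in a limited form. The four rules (Section 4.4, Section 7.2, Follow-up of Discontinuations and Section 7.3) need reconciling for unreachable participants. Once lost to follow-up is recorded, deaths and related SAEs up to year 5 may be missed. Participants who reappear may lose later titres.

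The size is unknown. Under the assumptions above, between 0.1 and 3.1 deaths might go unseen out of a small expected total, and avoidable titre loss runs from none to about 140 person-visits. All of this rests on assumed loss, death and return rates.

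Two stronger conclusions are tempting but unsupported. One is that the participants lost are those whose data matter most: nothing in the documents links loss of contact to death or waning antibody, and the threefold risk is only a stress case. The other is that the trial's main result is exposed. The affected endpoints are descriptive, and non-inferiority is tested on D29 data, before any yearly visit. This is an inexpensive improvement to the 5-year data, not a threat to the primary conclusion.

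**What to change.** Reconcile Protocol Sections 4.4, 7.2 (including Follow-up of Discontinuations) and 7.3 as follows:

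- In the yearly phase, record an unreachable participant who has not withdrawn consent as having missed that visit. Contact the participant again at each later yearly window and allow return to the schedule.
- Remove the no-enquiry sentence as far as deaths and related SAEs are concerned.
- Seek vital status at Y5 for everyone not known to have died and not withdrawn from consent, by means that respect participants' rights.
- In the SAP, report the number with unknown year-5 vital status by arm, next to the deaths in Table 7.8.

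Holding back the lost-to-follow-up label until the Y5 window has closed is one way to do this, but it is optional. The essential parts are re-contact, return and vital status.

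The cost is protocol and SAP wording, a few extra contact attempts per affected participant per year, and some untraceable participants carried as open for longer. Vital status for someone who does not answer may need a source other than a telephone call. No visit or procedure is added, and those who withdraw consent are unaffected.
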